Novelty and promise of the orexin system. The orexins are a class of recently discovered amino acid peptides concentrated in the hypothalamus with projections widely distributed throughout the brain. Two orexin receptors (OXR1, OXR2) have been identified. The orexin system is neuromodulatory, increasing neural action potentials via the regulation of glutamate and GABA. Its primary role appears to be in *energy homeostasis* (e.g., arousal, vigilance). Accordingly, antagonism (blockade) of OXR1 and OXR2 promotes sleep^{39,40}. In addition, there is strong preclinical and phase 1 evidence that orexin antagonists modulate three key cocaine-related variables documented above: sleep^{39,40}, stress/anxiety⁴¹⁻⁴³, reactivity to stimulant drug cues, including cocaine⁴⁴⁻⁴⁷. Only one approved FDA compound with specificity for the orexin receptor system (**suvorexant**) is currently available in the US market. It is indicated for treatment of insomnia. We propose that, due to the ability to regulate stimulant drug-cue reactivity, anxiety/stress, and sleep, suvorexant is an intriguing and potentially efficacious compound for the prevention of relapse in CUD.

Summary. Medications that attenuate drug cue reactivity (attentional bias, craving), reduce stress/anxiety, and enhance sleep quality may be effective pharmacotherapeutics for SUD. As these three factors all contribute to relapse, orexin receptor antagonists may be ideally suited to address the dynamic interaction of these factors, thereby helping in the prevention of relapse.

[figure not shown]
Overall Aim. According to the conceptual model posited in Figure 1, the overarching aim of this project is to conduct a first-in-human drug user study to examine the effects of the orexin antagonist suvorexant on drug-cue reactivity and its interactions with stress/anxiety and sleep.

HYPOTHESES and SPECIFIC AIMS

1. **Main effect:** To characterize the direct effect of suvorexant on drug cue reactivity. We hypothesize that suvorexant will significantly attenuate cocaine cue reactivity (attentional bias, craving).
2. **Stress/anxiety interaction:** To characterize the degree to which stress/anxiety mediates the effect of suvorexant on drug cue reactivity. We hypothesize an indirect effect of suvorexant on drug cue reactivity via stress/anxiety, such that attenuation of cocaine cue reactivity (attentional bias, craving) will be greater in those with larger reductions in stress/anxiety duration.

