Cue Reactivity: Cocaine Craving Questionnaire (CCQ)⁵⁵ is self-report 14-item measure with five conceptual domains: Desire to Use, Intention to Use, Anticipation of Positive Outcome, Anticipation of Relief from Dysphoria, and Lack of Control over use. The measure is well validated and has been used in multiple studies of CUD^{55,56}.

Sleep: Misfit Shine (Misfit © 2012). Sleep activity is monitored with a 3-axis accelerometer inside the watch device, using a general heuristic based on time and motion. The two primary data outcomes from sleep mode are total sleep and sleep quality (deep sleep duration). The device is waterproof and worn on the wrist 24 hrs per day. Data are downloaded to smartphone via Bluetooth.

Sleep: Pittsburg Sleep Quality Index (PSQI)⁵⁷. The PSQI is an 18-item self-report measure of sleep, providing a well-validated and reliable measure of sleep quality, latency, duration, duration efficiency, and disturbance, and an overall summary. It has been used in several studies of individuals with SUD, including cocaine^{21,58,59}.

Stress/Anxiety: Cold Pressor Test (CPT). The CPT reliably increases activity of the sympathetic nervous system and the HPA axis, and produces reliable increases in heart rate and cortisol^{75,76}. Subjects are requested to submerge the dominant arm up to the wrist or elbow in ice-cold water (0° to 4° C) for as long as possible with a maximum of 90 seconds. The procedure activates afferent nerves and elicits a CNS stress response^{75,76,77}. This procedure produces no lasting biological or psychological distress beyond the acute challenge period, and physiological effects return to baseline within 90 min⁷⁸. In fact, the CPT is used to study pain in children⁷⁹, and is considered a noninvasive, exempt educational experimental activity by the IRB of the University of Texas-Austin⁸⁰. It has been used extensively in cardiology, endocrinology, psychiatry, and psychology since 1940 as a challenge to the peripheral and central stress axis^{75,76}.

Stress/Anxiety: DASS21⁶⁰ is a 21-item self report questionnaire assessing the severity of clinically agreed upon core depression, anxiety, and stress symptoms. It is well validated in multiple languages and countries⁶¹, and has been utilized in SUD treatment and withdrawal studies⁶²⁻⁶⁴.

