Data Analyses. We will use multilevel modeling to evaluate cue reactivity (attentional bias, craving) as a function of suvorexant, time, and the interaction of suvorexant x time. Hypothesis evaluation will utilize both Frequentist and Bayesian methods. Power and sample size focus on the effect of suvorexant on drug cue reactivity (AB, CCQ). From a Frequentist perspective, assuming a correlation of $r = 0.5$ between measurement points and $\alpha = 0.05$, a sample of $N=30$ participants will provide 80% power to detect a moderate effect (Cohen’s $f = .0.24$) for the interaction if treatment and time. For Bayesian analyses, multilevel priors will be vague and neutral: coefficients ~Normal (mean = 0, variance = 1×10^6), level 1 variance ~ Gamma (shape=.001, scale=.001), level 2 variances ~ Uniform (0,100). Frequentist statistical models will utilize traditional mediation analyses as recommended by Baron and Kenny⁶⁸, which permits unbiased OLS estimates appropriate for this experimental design and sample size⁶⁹, and which we have utilized in previous published research⁷⁰. Bayesian statistical models will utilize path analysis (BSEM) to evaluate the mediating effects of stress/anxiety (biological and subjective-rated) and sleep (biological and subject-rated) for the effects of suvorexant on drug cue reactivity. An example of a mediation analysis using Bayesian SEM may be found Arbuckle⁷¹. Uncertainty surrounding the Bayesian estimate for the indirect effect employs the posterior distribution of the parameter (i.e. the product coefficient): a density denoting the probability that different values of the parameter obtain given the observed data. This approach may be particularly important for evaluating more complex mediation models (e.g. multiple mediators, latent variables) in the context of small sample sizes. Use of the MCMC (Monte Carlo Markov Chain) approach in Bayesian analyses has demonstrated superior small sample performance relative to maximum likelihood-based approaches in continuous, normally distributed data⁷². These properties are likely due to the MCMC approach’s lack of reliance on large sample size assumptions⁷³. BSEM prior specification will adapt recommendations from Muthén and Asparouhov⁷⁴.

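### The level-2 prior is bounded on the variance, so it caps the between-subject SD at 10 raw units; if a summed or percent score varies that much, Bayesian intervals for arm differences in level are too narrow

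*Combined protocol and SAP*

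**What the plan says.** Data Analyses plans multilevel models of attentional bias and craving "as a function of suvorexant, time, and the interaction of suvorexant x time", evaluated by both frequentist and Bayesian methods. For the Bayesian models it states that "multilevel priors will be vague and neutral", and gives three: Normal coefficients with mean 0 and variance 1×10^6, "level 1 variance ~ Gamma (shape=.001, scale=.001"), and "level 2 variances ~ Uniform (0,100"). Priors for the Bayesian path models used for mediation are covered in a separate sentence of the same section.

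The scale of the outcomes is left open. Measurements describes the craving questionnaire as a "self-report 14-item measure with five conceptual domains", without a response range or a scoring rule (sum or item mean). Attentional bias is an anti-saccade error rate, with no statement of percent or proportion. No SD is given for either outcome, nothing says that they will be standardised, and the random-effect structure is not stated.

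**The concern.** A prior on a variance is vague only relative to the scale of the outcome. Uniform(0,100) on an SD would be wide for any plausible scoring here. On a variance it is a hard ceiling at SD 10 that no amount of data can move. If the true between-subject SD exceeds 10, the posterior piles up against the ceiling, part of the real variation between subjects is denied, and part of it moves into the residual.

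Aim 1 is "To characterize the direct effect of suvorexant on drug cue reactivity" and is labelled a main effect, so differences in level between arms are of interest. The Bayesian interval for such a difference could be too short for a reason unrelated to the data, and could differ between two scorings of the same questionnaire. The frequentist and Bayesian answers could then disagree because of a prior bound.

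**Working it through.** **1. Inputs.** From the documents: N = 30 completers, two arms, cue reactivity on days 1, 7 and 14, r = 0.5 between visits, α = 0.05, f = 0.24 for treatment by time, and the priors above. Assumed: 1:1 allocation (15 per arm), random intercepts only, and a range of total SDs, because none is given.

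**2. The plan's own figure.** For the within-between interaction, λ = f²·N·m/(1 − r) = 0.0576 × 30 × 3 / 0.5 = 10.37 on 2 and 56 df. Power is 80.8%, so the stated 80% is reproduced with three visits.

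**3. Where the cap binds.** Maximum between-subject SD = √100 = 10. With r = 0.5 the between-subject variance is half the total, so the cap equals the true value at total SD 10/√0.5 = 14.1.

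**4. Can the outcomes get there?** The largest possible SD of a bounded score is half its range.
- Proportion: 0.5. Item mean on an assumed 1–7 response: 3. Neither can reach 10.
- Percent: 50. Sum of 14 items on an assumed 1–7 response (14 to 98): 42. Either could reach 10, but the documents do not show that it would.

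**5. Simulation.** 1,000 trials per setting, grid posterior from the between- and within-subject sums of squares (28 and 56 df), flat fixed effects, Gamma(.001, rate .001) on the level-1 precision. Coverage of nominal 95% intervals is given as visit-averaged difference / day-14 difference / change from day 1 to day 14 between arms. The width ratio is variance prior over SD prior, in the same order.

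| Total SD (r = 0.5) | Uniform on variance | Uniform on SD | Width ratio |
|---|---|---|---|
| 10 | 94.7 / 95.5 / 95.9% | 94.3 / 95.8 / 95.7% | 0.99 / 0.99 / 1.00 |
| 14.1 | 91.6 / 93.8 / 96.3% | 94.4 / 95.5 / 95.9% | 0.87 / 0.92 / 1.01 |
| 20 | 87.8 / 92.7 / 97.6% | 94.1 / 95.2 / 96.0% | 0.75 / 0.87 / 1.08 |
| 30 | 83.8 / 93.2 / 98.6% | 94.5 / 95.4 / 96.1% | 0.69 / 0.90 / 1.23 |

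At total SD 20 with r = 0.8, coverage under the variance prior is 77.7 / 85.0 / 98.2%.

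**6. Hand check at total SD 20.** True variances are 200 within and 200 between.
- Visit-averaged difference: correct width = 3.92·√[(200/3 + 200)·2/15] = 23.4. Under the cap the mean level-1 estimate rises to about 245. Even with the between-subject variance exactly at 100, width = 3.92·√[(245/3 + 100)·2/15] = 19.3.
- Change between arms: correct width = 3.92·√(4·200/15) = 28.6; with 245 it is 31.7.

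Both directions agree with the simulation. As an approximation, multiplying the critical F by 1.08² takes the interaction power from 80.8% to about 75%.

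**7. The level-1 prior read literally.** Gamma with shape .001 and scale .001 on the variance s contributes −0.999·ln s − 1000·s to the log posterior. At total SD 20 the within-subject sum of squares is about 56 × 200, which contributes −28·ln s − 5600/s. Setting the derivative to zero gives 1000s² + 29s − 5600 = 0, so s ≈ 2.35 against a true 200. The interaction interval is then 3.92·√(4·2.35/15) = 3.1 wide against 28.6, and coverage is about P(|Z| < 1.96·√(2.35/200)) = 17%, whichever level-2 prior is used. Standardising lessens this but does not remove it: with total SD 1 the equation is 1000s² + 29s − 14 = 0, so s ≈ 0.105 against 0.5, and coverage is about 63%.

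**The case against.** The strongest reply is about relevance. The plan powers treatment by time, and for that term, under a conventional level-1 prior, the cap makes the interval slightly conservative. The contrast that suffers most averages over day 1, which appears to be before dosing: visits are at 10 AM, doses at 10 PM, and the Study design table collects no compliance or side-effect data at the first visit. The day-14 difference, a more relevant contrast, loses only about 2.5 points of coverage at total SD 20. This stands, and it limits the size of the point.

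A reader might infer that any summed or percent score will give intervals that are too narrow, or that the drug effect will be declared too often. The documents support neither. The scale alone is not enough, no SD is given, and at total SD 10 the cap does almost nothing. Nor do they show that the answer to the first hypothesis would change: the frequentist multilevel test is untouched, the path-model priors are set separately, and no rule makes the Bayesian interval decisive.

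It may also be said that the SD and the precision were meant, as shorthand. That is possible, but a programmer following the text would code the variance in both places. A consistently literal reading does not help either: the interaction interval then becomes far too narrow instead of too wide (step 7).

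Finally, the plural in the level-2 prior may include slopes. If random slopes are fitted and their SD exceeds 10 units per unit of time, the interaction interval could narrow too. This cannot be settled from the documents.

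**Conclusion.** The point holds conditionally. As written, the level-2 prior is a hard bound at a between-subject SD of 10 raw units, and calling it vague is right only if the outcomes are on a small scale. With item-mean or proportion scoring the bound has no effect. With a between-subject SD of about 10 or more, Bayesian intervals for arm differences in level are too narrow: at an assumed total SD of 20 and r = 0.5, coverage is about 88% for the visit-averaged difference (interval about 25% narrower) and about 93% at day 14, while the powered interaction interval is about 8% too wide. These figures rest on 15 per arm, complete data, random intercepts only and a conventional vague level-1 prior. The level-1 Gamma needs correcting in the same sentence, because its literal form damages the interaction intervals on any of the scales examined. The correction is worth making because it is nearly free, not because a wrong result has been shown.

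**What to change.** - Place Uniform(0,100) on the level-2 standard deviations, or standardise attentional bias and craving to the pooled day-1 SD before fitting.
- Place the Gamma(.001, .001) on the level-1 precision and state that the second .001 is a rate. This is needed under either option above.
- State how each outcome is scored and which random effects are fitted.
- Report a check that no posterior for a variance or SD sits at a prior bound.

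The cost is a few words in Data Analyses and a line or two of model code. No change to design, sample size or data collection is needed.

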3. **Sleep interaction:** To characterize the degree to which sleep mediates the effect of suvorexant on drug cue reactivity. We hypothesize an indirect effect of suvorexant on drug cue reactivity via sleep, such that attenuation of cocaine cue reactivity (attentional bias, craving) will be greater in those with larger improvements in sleep duration.

*Conceptual Model:
Orexin System Effects on Relapse Risk*

Figure 1. Summary of Conceptual Model

Research Plan

Our group at the University of Texas Center for Neurobehavioral Research on Addiction (CNRA) has developed, utilized, and validated laboratory models of drug relapse, allowing us to examine pharmacotherapeutic and cognitive-behavioral interventions for relapse prevention.

Study design. To accomplish the project aims, we will utilize a mixed-model experimental design, with a between-groups factor of dose (suvorexant vs. placebo) and a within-subjects factor of time. Subjects will receive suvorexant (**10 mg week 1, 20 mg week 2**) or placebo PO, once daily at 10 PM. Medication condition will be double-blind, with urn-randomized assignment to dose condition balanced by gender and severity of cocaine use. A summary of timelines and measures is shown in the Table below.

Mon	Wed	Fri	Mon	Wed	Fri	Mon
1,4,5,6,7	1,2,3,4,5	1,2,3,4,5	1,2,3,4,5,6,7	1,2,3,4,5	1,2,3,4,5	1,2,3,4,5,6,7
Key: (1) Provide medication (MEMS bottle); (2) Compliance data for medication adherence (MEMS, pill count, riboflavin, text message); (3) Side effects data, med check, UA toxicology; (4) Sleep data; (5) stress /anxiety data; (6) acute stressor challenge (cold pressor); (7) Cue reactivity data						

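### The mediation estimates for Aims 2 and 3 are described as unbiased, but only dose is randomised, and the frequentist limb gives no interval for the indirect effect

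*Combined protocol and SAP*

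**What the plan says.** Under Hypotheses and Specific Aims, Aims 2 and 3 each hypothesise an indirect effect of suvorexant on cue reactivity, the first through stress/anxiety and the second through sleep.

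The Data Analyses section covers the analysis in three places:

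- **Main effect.** "We will use multilevel modeling to evaluate cue reactivity (attentional bias, craving) as a function of suvorexant, time" and their interaction. This model is not linked to the mediation aims.
- **Frequentist mediation.** "Frequentist statistical models will utilize traditional mediation analyses as recommended by Baron and Kenny", an approach which "permits unbiased OLS estimates appropriate for this experimental design and sample size". The section names no test or interval for the indirect effect here, and no mediator-outcome assumption.
- **Bayesian mediation.** A path model, whose uncertainty for the indirect effect "employs the posterior distribution of the parameter (i.e. the product coefficient"). This is the only place where uncertainty for the product of paths is described.

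On how the two limbs combine, the section says only: "Hypothesis evaluation will utilize both Frequentist and Bayesian methods".

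Under Study design, the one thing allocated at random is the drug: "urn-randomized assignment to dose condition balanced by gender and severity of cocaine use". Stress/anxiety and sleep are observed, not assigned.

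**The concern.** An indirect effect is the product of two paths: drug to mediator (a), and mediator to outcome with the drug held fixed (b). Randomisation supports a causal reading of a and of the total effect. It says nothing about b. People who sleep badly or are more stressed may crave more for reasons unrelated to the drug. The protocol's background makes such common causes plausible, since its Sleep in addiction paragraph describes sleep and severity of cocaine use as affecting each other.

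If suvorexant lowers cue reactivity directly and also shifts sleep or stress, a confounded b turns part of the direct effect into apparent mediation. The Bayesian path model shares the problem, because a posterior for the product inherits whatever b estimates. Calling the estimates unbiased hides the assumption on which both limbs depend. Without an interval for the product, the frequentist limb also offers no statement of how uncertain the indirect effect is at N = 30.

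**Working it through.** **1. The plan's own figure.** The only power statement concerns the treatment-by-time interaction: N = 30 "participants will provide 80% power to detect a moderate effect" (f read as 0.24, r = 0.5, alpha = 0.05). With 2 arms and 3 cue-reactivity visits (days 1, 7 and 14):

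- lambda = f² × N × m / (1 − r) = 0.0576 × 30 × 3 / 0.5 = 10.37, on 2 and 56 degrees of freedom.
- Power = 80.8%, so the stated 80% reproduces. It does not cover the indirect effects.

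The day-14 arm difference d implied by f = 0.24 depends on the time pattern:

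- Differences 0, d, d: f = d/√18, so d = 0.24 × 4.243 = 1.02 SD.
- Differences 0, d/2, d: f = d/√24, so d = 0.24 × 4.899 = 1.18 SD.

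These are used below as the direct drug effect.

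**2. Assumptions, because the documents give no mediation path sizes.** There are 15 participants per arm. Mediator and outcome each have unit within-arm variance, half of it stable and half visit-specific, which gives r = 0.5 within each measure. The true mediator effect is zero. The within-arm mediator-outcome correlation is 0.30, from unmeasured causes. The drug shifts the mediator by a = 0.4 to 1.2 SD. False mediation means that the total effect, path a and path b all have p < 0.05.

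**3. Expected mediator slope.**

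- Raw day-14 values: b = cov(M,Y)/var(M) within arm = 0.30/1 = 0.30. The apparent indirect effect is a × b: 0.12 at a = 0.4, 0.24 at 0.8 and 0.36 at 1.2, against a true value of 0.
- Change scores: var = 2 × 0.5 = 1, and cov = 2 × the visit-specific covariance. So b = 0 if the 0.30 is wholly stable, 2 × 0.15 = 0.30 if it is half and half, and 2 × 0.30 = 0.60 if it is wholly visit-specific.
- Adjustment for both day-1 values, with t the stable covariance: put e₊ = 1.3 − (0.5 + t)²/1.3, e₋ = 0.7 − (0.5 − t)²/0.7, and b = (e₊ − e₋)/(e₊ + e₋). For t = 0.30, (0.808 − 0.643)/1.451 = 0.11. For t = 0.15, (0.975 − 0.525)/1.500 = 0.30. For t = 0, (1.108 − 0.343)/1.451 = 0.53.

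**4. Simulated false mediation** (10,000 trials per cell, a = 0.8-1.2 SD, direct effect 1.02-1.18 SD).

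| Source of the 0.30 | Raw day 14 | Day-1-adjusted | Change scores |
|---|---|---|---|
| Stable | 15-28% | 4-8% | 2-4% |
| Half stable, half visit-specific | 15-28% | 18-29% | 15-28% |
| Wholly visit-specific | 15-28% | 51-75% | 47-77% |

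At a = 0.4 SD the raw figure is about 5-6%. The slope stays at 0.30 there, but path a is seldom significant.

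**5. A separate simulation with no direct drug effect** (a = 0.8, 30% of residual variance shared, true b = 0) also gives a mean indirect effect of about 0.24. Both paths are significant in 20% of trials, and all three steps in about 1%.

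**The case against.** Several points on the other side are fair.

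- *The word unbiased may refer to a finite-sample property of OLS.* It can be read that way. The aims are causal, however, and that property does not carry over to a causal indirect effect. The unstated assumption is the real point.
- *The cited mediation source may supply a test.* That cannot be checked here. The point is only that the Data Analyses section states none.
- *The rates depend on assumed inputs.* This stands. At a mediator shift of 0.4 SD the rate is about 5-6%. With no direct drug effect and a total-effect requirement, it is about 1%. The bias in the slope does not depend on the mediator shift; the frequency of false claims does.

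A reader might also infer three stronger things, which the documents do not support.

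- *That ignoring day-1 values is the error and using them the remedy.* Adjustment or change scores help against stable confounding, do nothing useful when it is half visit-specific, and make matters worse when it is wholly so. The documents do not say which case applies.
- *That the two limbs will often contradict each other.* A disagreement of 32-45% can be produced, but only by requiring a significant total effect in one limb and not in the other, with the effect running wholly through the mediator. Without that requirement the limbs disagree in 2-5% of trials. The larger figure measures the requirement, not the choice of limb.
- *That the main effect of Aim 1 is biased.* It is not touched, because dose is randomised.

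**Conclusion.** The concern holds for the indirect effects of Aims 2 and 3. Unbiasedness is not a property of those estimates in this design, in either limb, because the mediator-to-outcome path is not randomised. The frequentist limb also lacks a stated interval for the quantity that it is meant to evaluate.

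The size is conditional. With a within-arm correlation of 0.30 from unmeasured causes and a direct drug effect at the planning size, the raw mediator slope averages 0.30 against a truth of zero. False mediation then ranges from about 5-6% (mediator shift 0.4 SD) to 15-28% (0.8-1.2 SD). Neither day-1 adjustment nor change scores is unbiased in general. The unnamed visit, scale and deciding limb are secondary: they are missing detail that should be fixed in advance, and do not by themselves show that the analysis is wrong.

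**What to change.** In the Data Analyses section:

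1. Replace the claim of unbiased estimates with wording such as: *the indirect effect assumes no unmeasured mediator-outcome confounding, which randomisation of dose does not ensure*. Apply it to both limbs.
2. Report the frequentist indirect effect as the product of paths with a 95% percentile bootstrap interval, resampling participants within arm.
3. Add a sensitivity analysis that reports the indirect effect over an assumed residual correlation between the mediator and outcome equations, for example 0 to 0.5, and states where its interval reaches zero.
4. As supporting prespecification, name one mediator measure, visit and scale for each aim, use them in both limbs, and say which limb decides. This is not a recommendation of day-1 adjustment or change scores.
5. State whether a significant total effect is required, as an acknowledged trade-off. In the separate simulation without a direct effect, requiring it cuts false mediation from 20% to about 1%. It also cuts power for a true, fully mediated effect (a = 0.8, b = 0.5) from about 39% to 9%.
6. Optionally, repeat the analysis with the mean of the week-2 Wednesday and Friday mediator values. This is possible only for sleep and the stress/anxiety questionnaires. The cold pressor, cardiovascular and cortisol measures are scheduled only on days 1, 7 and 14 (Subject participation requirements).

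The cost is wording and a few lines of code, with no new data or visits. The mediation conclusion becomes more cautious.
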